10.2.2 Sensitivity Analysis for Possible Violation of Normality Assumption

10.2.3 Sensitivity Analyses in Missing Data Handling

ANCOVA Model Based on 3-month Average of the Monthly Migraine Days

The response variable for the ANCOVA model is the change from baseline in the 3-month average of the monthly migraine days for each participant. The ANCOVA model includes terms for treatment, prior exposure (yes/no) to a migraine prevention medication with proven efficacy, and baseline score. The treatment difference for atogepant doses versus placebo will be estimated and reported along with the corresponding 95% CI and nominal p-value for superiority testing. This analysis was recommended by FDA at the End of Phase 2 meeting and termed as supportive analysis. There are no missing data based on this derivation because patients who discontinued the treatment are assumed to maintain the same mean (observed while on treatment) for 3 months (12 weeks).

Within-group Imputation Based on Observed Data

Sensitivity analysis will be performed based on imputation using participants from the same treatment group with observed data under the MAR assumption. The details of imputation are as follows

Allergan	SAP 3101-301-002 AGN-241689

MMRM Based on Primary Measures Collected during the Double-blind and Follow-up **Periods**

The details for this analysis are provided in Section 10.5.

10.3 Secondary Efficacy Endpoints

The secondary efficacy endpoints for the United States and the EU are as follows:

- Change from baseline in mean monthly headache days across the 12-week treatment period.
- Change from baseline in mean monthly acute medication use days across the 12-week treatment period.
- \geq 50% reduction in 3-month average of monthly migraine days
- Change from baseline in MSQ v2.1 Role Function Restrictive domain score at Week 12.
- Change from baseline in mean monthly Performance of Daily Activities domain score of the AIM-D across the 12-week treatment period.
- Change from baseline in mean monthly Physical Impairment domain score of the AIM -D across the 12-week treatment period.

The secondary endpoints for headache days, acute medication use days, Performance of Daily Activities domain score of the AIM-D, and Physical Impairment domain score of the AIM-D will be analyzed in the same manner as that used to analyze the primary endpoint. For MSO v2.1 Role Function Restrictive domain score, the analysis will be performed similarly to the primary MMRM, with focus on the pairwise contrasts of each dose group to placebo at Week 12. Week

[figure not shown]
Allergan	
7 the gan	

SAP 3101-301-002 AGN-241689

16 (follow-up visit) data for MSQ v2.1 Role Function Restrictive domain score will not be included in MMRM analysis, and only summary statistics for Week 16 will be provided. The corresponding sample SAS code is given as follows

The 50% responder, defined as a participant with at least a 50% reduction from baseline in the 3-month average of monthly migraine days, will be assessed for each individual. A logistic regression model will be used to analyze the 50% responders across the 12-week treatment period. This model assumes a binary distribution for the response and uses a logit link. The analysis model will include treatment group, prior exposure (yes/no) to a migraine prevention medication with proven efficacy, and baseline monthly migraine days. The treatment difference in terms of odds ratio between each atogepant dose group and placebo will be estimated and tested from this model. The sample SAS is given as follows

[figure not shown]
Allergan		SAP 3101-301-002 AGN-241689

Allergan	SAP 3101-301-002 AGN-241689

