#### **Copy-reference Approach**

The Copy-reference Approach will be performed on the primary endpoint to assess the robustness of the MMRM analysis to possible violation of the missing-at-random (MAR) assumption. This sensitivity analysis is one type of pattern-mixture models (PMM), under which data could be missing-not-at-random (MNAR), with repeated analyses combined via the reference based multiple imputation (MI) procedure. Participants who discontinued in the Atogepant groups are assumed to have no treatment effect after the discontinuation. Participants are assumed to copy the profile of placebo arm and missing values are imputed based on the distribution estimated from the placebo group under the MAR using copy-reference approach.

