#### **7.4.6 Off-treatment Hypothetical Estimand Approach for the Secondary Endpoints**

Continuous secondary endpoints will be handled using the same estimand approach defined above for the primary endpoint.

The secondary endpoint of 50% responders will be derived using both on-treatment and off-treatment observed data as defined in the primary endpoint above. The population-level summary for this endpoint is the odds ratio for each atogepant group relative to placebo.

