The Safety Population includes all participants who received at least 1 dose of study intervention. All safety analyses will be performed using the Safety Population and based on the treatment actually received, regardless of assigned treatment according to the planned randomization. Participants will be summarized according to the study treatment received for the majority of treatment period.

The Modified Intent-to-Treat (mITT) Population includes all randomized participants who received at least 1 dose of study intervention, had an evaluable baseline period of eDiary data and had at least 1 evaluable post-baseline 4-week period (Weeks 1 to 4, 5 to 8, and 9 to 12) of eDiary data during the double-blind treatment period. All efficacy analyses described in Sections 10.2 - 10.4 will be performed using the mITT population and based on the randomization assignment, regardless of the actual treatment received. All efficacy analyses will be conducted using mITT population unless specified otherwise.

The analysis population for Off-treatment Hypothetical Estimand includes all randomized participants who received at least 1 dose of study treatment, had an evaluable baseline period of eDiary data and had at least 1 evaluable post-baseline 4-week period (Weeks 1 to 4, 5 to 8, 9 to 12) of eDiary data during the DB treatment period and follow-up period, regardless of whether on study treatment or off study treatment.

7 Participant Disposition

The number of participants in the ITT, Safety, and mITT Populations will be summarized by treatment group; the number of participants screened will be summarized for overall only. The number of participants in the ITT Population will also be summarized by treatment group for the

SAP 3101-301-002 AGN-241689

following factors: 1) Randomization stratification factor (prior exposure [yes/no] to a migraine prevention medication with proven efficacy) from IWRS; 2) Prior exposure to migraine prevention medication with proven efficacy based on prior medication collected from eCRF, which will be termed as "actual strata" in the SAP. The list of participants with incorrect randomization stratum will be provided.

[figure not shown]

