10.5 Off-treatment Hypothetical Estimand

This section defines an estimand

Per study design (Protocol Sections 8.4.3.1 and 8.8), eDiary data will be collected for participants who early terminated from the double-blind treatment period during the 4 weeks between V7 (Early termination visit) and V8 (Follow-up Visit), i.e., participants who prematurely discontinued (before Week 12) will continue to complete eDiary efficacy assessments while offtreatment.

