10.5.4 Accounting of Intercurrent Events

Intercurrent events and their handling rules are as follows:

- Participants who started a new migraine prophylaxis treatment during the double-blind or safety follow-up period will have their data during the follow-up period after starting the new migraine prophylaxis treatment excluded from the analysis.
- Participants who discontinue study treatment due to all reasons other than starting a new migraine prophylaxis treatment will have their data collected after discontinuation of study treatment, and those off-treatment data will be included in the analysis.

If a participant provides less than 14 days of efficacy data during a monthly period regardless in the double-blind treatment period or the follow-up period, then he/she is considered to have missing data during that monthly period. When a participant provides at least 14 days of efficacy

Allergan SAP 3101-301-002 AGN-241689

data during a monthly period, he/she is considered to have efficacy data during that monthly period.

As the protocol prohibits participants from starting any new prophylaxis treatment until the study is completed. Only a limited number of participants as protocol deviators might take new prophylaxis treatment during the study. The criteria for identifying the participants who started a new migraine prophylaxis treatment are described in Section 17.11.

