10.5.6 Off-treatment Hypothetical Estimand Approach for the Secondary Endpoints

Continuous secondary endpoints based on eDiary data will be handled using the same estimand approach defined above for the primary endpoint.

The secondary endpoint of 50% responders are derived at least a 50% reduction from baseline in the 3-month average of monthly migraine days using data collected from the double-blind period and follow-up period. Data after participants started a new prophylaxis treatment during the follow-up period will be excluded. The population-level summary for this endpoint is the odds ratio from a logistic regression for each atogepant group relative to placebo with baseline monthly migraine days as a covariate, prior exposure (yes/no) to a migraine prevention medication with proven efficacy and treatment group as fixed factors.

The graphical approach to control the overall Type I error rate described in Section 10.3 will be provided for primary and key secondary endpoints in the analysis population for off-treatment hypothetical estimand.

11 Safety Analyses

The safety analysis will be performed using the Safety Population. The safety parameters will include adverse events (AEs), clinical laboratory, vital sign, electrocardiographic (ECG), and C-SSRS. For clinical laboratory, vital sign, and ECG, the last non-missing safety assessment before the first dose of treatment will be used as the baseline for all analyses of that safety parameter. Continuous variables will be summarized by number of participants and mean, SD, median, Q1, Q3, minimum, and maximum values. Categorical variables will be summarized by number and percentage of participants.

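### Does the 50% responder endpoint need a further missing-data analysis because early stoppers may be classified on their on-treatment months?

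*SAP*

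**What the plan says.** The 50% responder rate is Secondary 3 and is tested within the graphical procedure at an overall 0.05 (Protocol 7.3.2; SAP Table 18-1). SAP 10.3 classes as a responder "The 50% responder, defined as a participant with at least a 50% reduction from baseline in the 3-month average of monthly migraine days" and analyses it by logistic regression. The mITT population of SAP Section 6 asks only that the participant "had at least 1 evaluable post-baseline 4-week period (Weeks 1 to 4, 5 to 8, and 9 to 12) of eDiary data" in the double-blind period.

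SAP 10.2.3, describing the supportive ANCOVA on the change in the 3-month average, states: "There are no missing data based on this derivation because patients who discontinued the treatment are assumed to maintain the same mean", namely the mean seen on treatment, for all 12 weeks. It adds that FDA recommended this analysis.

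Data after stopping enter through the off-treatment hypothetical estimand:

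- Protocol 7.4.6: "The secondary endpoint of 50% responders will be derived using both on-treatment and off-treatment observed data".
- SAP 10.5.6 defines response by a reduction "in the 3-month average of monthly migraine days using data collected from the double-blind period and follow-up period" and applies the graphical procedure to the primary and key secondary endpoints in that population.
- SAP 10.5: "eDiary data will be collected for participants who early terminated from the double-blind treatment period during the 4 weeks between V7" and Visit 8. Protocol 8.8 places Visit 8 four weeks after the last dose.
- SAP 10.5.4: "If a participant provides less than 14 days of efficacy data during a monthly period", that month is missing.

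On reference-based imputation, Protocol 7.3.1.1 says: "The Copy-reference Approach will be performed on the primary endpoint".

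**The concern.** Three features together look like a gap. First, a multiplicity-controlled endpoint that readers will take as 12-week response has no visible rule for participants without all three months. Second, the rule given for the same average in the ANCOVA credits a discontinuer with the on-treatment benefit for the rest of the 12 weeks. If that benefit is lost on stopping and the active arms lose participants, the responder difference is flattered. Third, the off-treatment analysis follows the diary for only four weeks after the last dose, so it has no evaluable Month 3 for early stoppers. Copy-reference imputation, which would test the assumption directly, is specified for the primary endpoint only. At stake is the size, and in a close case the significance, of a labelled secondary result.

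**Working it through.** **The plan's own figure.** Inputs from SAP Section 15: n = 218 per arm, rates 33% and 50%, two-sided alpha 0.0167 (z = 2.393). The pooled rate is 0.415.

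- SE under the null = √(2 × 0.415 × 0.585 / 218) = 0.0472.
- SE under the alternative = √((0.33 × 0.67 + 0.50 × 0.50) / 218) = 0.0465.
- Power = Φ((0.17 − 2.393 × 0.0472) / 0.0465) = Φ(1.227) = 0.890.

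The stated 89% reproduces.

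**Which months can be evaluated.** Months are Days 1–28, 29–56 and 57–84 (Protocol 7.2), and a month needs 14 reported days. Let L be the day of the last dose, with a complete diary that ends at L for double-blind data and at L + 28 for off-treatment data.

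- Double-blind data: Month 2 needs L − 28 ≥ 14, so L ≥ 42. Month 3 needs L − 56 ≥ 14, so L ≥ 70.
- With off-treatment data: Month 2 needs (L + 28) − 28 ≥ 14, so L ≥ 14. Month 3 needs (L + 28) − 56 ≥ 14, so L ≥ 42. L = 41 gives 13 days.

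The Day 42 threshold is therefore right. It moves earlier if the four weeks run from an early-termination visit held after the last dose: a 7-day lag, which is assumed, gives Day 35. For a last dose on Days 14–41, the off-treatment data do supply Month 2. That month lies wholly after stopping when L ≤ 28, and partly after stopping when L is 29–41.

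If L is uniform over Days 14–83 (70 days), Month 3 is lacking in the double-blind data for Days 14–69, 56/70 = 80% of discontinuers. With off-treatment data it is lacking for Days 14–41, 28/70 = 40%.

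**Size of the bias.** The documents give no dropout rate, so everything here is assumed. The model has a baseline of 7.5 days, monthly SD 3.5, within-person correlation 0.5 to 0.8, full-data response set to 50% and 33%, placebo-like months after stopping, and averaging of the months available. It was simulated with 1,000,000 participants per arm. Entries are percentage points by which the difference is overstated, with L uniform over Days 14–83.

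| Dropout, active / placebo | On-treatment mean carried forward |
|---|---|
| 10% / 10% | 0.6–0.7 |
| 15% / 15% | 0.9–1.0 |
| 15% / 5% | 1.0–1.1 |
| 5% / 15% | 0.1–0.3 |

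Across these rows the off-treatment version leaves 0.0–0.2. If every discontinuer stops on Days 14–41 (correlation 0.65), the ranges are 0.3–1.6 carried forward and 0.1–0.4 off-treatment.

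**Would a non-responder rule be a better check?** Count everyone without an evaluable Month 3 as a non-responder, and suppose they would otherwise have responded at their arm's rate. The difference is 50% × (1 − dA) − 33% × (1 − dP), where dA and dP are the shares affected.

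- 15% active, 5% placebo: 42.5 − 31.35 = 11.15 points. With all stops on Days 14–41 the model's true difference is about 15.3, so the rule is off by about −4.1. Carry-forward is off by about +1.6.
- 5% active, 15% placebo: 47.5 − 28.05 = 19.45 points. The true difference is about 16.4, so the rule is off by about +3.0. Carry-forward is off by about +0.2 to +0.3.

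With unequal dropout the rule errs by more than the assumption it is meant to test.

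**The case for a change.** The best case for a change is that it would be cheap and that the public text really does leave a choice open. Averaging the available months is arithmetically the same as carrying their mean forward. Excluding such participants, or counting them as non-responders, would give different answers in a controlled test. For early stoppers Month 3 is not evaluated in any visible analysis of this endpoint. Since dropout by arm cannot be known in advance, a copy-reference version of Secondary 3 could be fixed beforehand for little cost.

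The arithmetic behind this stands, and so does the observation that the visible rule is incomplete. Three things limit it. The derivation section (SAP 17.2.1) and the text after the responder code in SAP 10.3 are blacked out, so neither the rule nor a further sensitivity analysis can be called absent. The off-treatment analysis is more than a side check: it carries its own graphical procedure, and Protocol 7.1 uses the term primary efficacy analysis population, with a redacted qualifier, for a population that includes follow-up data. Finally, Month 3 is not left on one untested assumption. When available months are averaged, the value standing in for Month 3 is the on-treatment mean in one analysis and includes off-treatment Month 2 data in the other.

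**Conclusion.** No change to the plan follows. What is visible is at most missing detail about how the average is formed. Analysts would fill it in the ordinary way, by averaging the evaluable months, and the redacted derivation may already say so. SAP 10.2.3 openly states its carry-forward as an assumption, so rewording it would change no result.

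Under assumed dropout of 5% to 15% per arm, with reversion to placebo-like months, the possible overstatement is 0.1 to 1.1 points of the planned 17, or about 1.6 in the extreme where everyone stops before Day 42. The off-treatment analysis already planned brings this down to 0.0 to 0.4 points. A non-responder analysis would be a trade-off with larger errors when dropout is unequal. Copy-reference imputation for Secondary 3 would be a reasonable optional extra if the redacted text lacks it, but the conclusion on this endpoint does not depend on it.

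The sizes rest on the assumed baseline, SD, correlation and timing of stopping. Much heavier or more unequal early dropout than the range tried would give larger figures. The Day 42 threshold and the 89% power use only the documents' own numbers.

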10.4 Additional Endpoints

[figure not shown]

Allergan	SAP 3101-301-002 AGN-241689

Allergan	SAP 3101-301-002 AGN-241689

10.5 Off-treatment Hypothetical Estimand

This section defines an estimand

Per study design (Protocol Sections 8.4.3.1 and 8.8), eDiary data will be collected for participants who early terminated from the double-blind treatment period during the 4 weeks between V7 (Early termination visit) and V8 (Follow-up Visit), i.e., participants who prematurely discontinued (before Week 12) will continue to complete eDiary efficacy assessments while offtreatment.

10.5.1 Treatment Condition of Interest

Participants take assigned treatment by randomization during the double-blind treatment period. In addition, permissible and prohibited mediations are described below:

- Participants are allowed to take acute migraine medications (Protocol Section 4.4.1) to keep the participants in the study.
- The protocol prohibits patients from starting any new migraine preventive treatments (Protocol Section 4.4.2) during the study (including the double-blind treatment period and the follow-up period).

10.5.2 Population

The target population is patients suffering from migraine with aura or migraine without aura satisfying the inclusion and exclusion criteria as specified in Section 4 of protocol.

The analysis population for off-treatment hypothetical estimand is defined to be all randomized participants who received at least 1 dose of study treatment, had an evaluable baseline period of eDiary data and had at least 1 evaluable post-baseline 4-week period (Weeks 1 to 4, 5 to 8, 9 to 12) of eDiary data, regardless of whether on study treatment or off study treatment.

On

study treatment is from the first dose till the last dose of study intervention. As the analysis-visit mapping window (Table 17–2) is defined for the entire postbaseline period (not limited to the double-blind treatment period for participants who prematurely discontinued), the number of participants in the analysis population for off-treatment hypothetical estimand is expected to be greater than or equal to the number of participants in the mITT Population.

10.5.3 Variable

The variable is the same as the primary efficacy endpoint defined in Section 10.2, which is the change from baseline in the participant's mean monthly (4-weeks) migraine days across the 12-week treatment period as derived from the eDiary data.

10.5.4 Accounting of Intercurrent Events

Intercurrent events and their handling rules are as follows:

- Participants who started a new migraine prophylaxis treatment during the double-blind or safety follow-up period will have their data during the follow-up period after starting the new migraine prophylaxis treatment excluded from the analysis.
- Participants who discontinue study treatment due to all reasons other than starting a new migraine prophylaxis treatment will have their data collected after discontinuation of study treatment, and those off-treatment data will be included in the analysis.

If a participant provides less than 14 days of efficacy data during a monthly period regardless in the double-blind treatment period or the follow-up period, then he/she is considered to have missing data during that monthly period. When a participant provides at least 14 days of efficacy

Allergan SAP 3101-301-002 AGN-241689

data during a monthly period, he/she is considered to have efficacy data during that monthly period.

As the protocol prohibits participants from starting any new prophylaxis treatment until the study is completed. Only a limited number of participants as protocol deviators might take new prophylaxis treatment during the study. The criteria for identifying the participants who started a new migraine prophylaxis treatment are described in Section 17.11.

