## **MMRM Based on Primary Measures Collected during the Double-blind and Follow-up Periods**

The details for this analysis are provided in Section 7.4.

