### 7.4.1 Treatment Condition of Interest

Participants take assigned treatment by randomization during the double-blind treatment period. In addition, permissible and prohibited mediations are described below:

- Participants are allowed to take acute migraine medications (Protocol Section 4.4.1) to keep the participants in the study.
- The protocol prohibits patients from starting any new migraine preventive treatments (Protocol Section 4.4.2) during the study (including the double-blind treatment period and the follow-up period).

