#### **7.4.4 Accounting of Intercurrent Events**

Intercurrent events and their handling rules are as follows:

- Participants who started a new migraine prophylaxis treatment during the double-blind or safety follow-up period will have their data during the safety follow-up period after starting the new migraine prophylaxis treatment excluded from the analysis.
- Participants who discontinue study treatment due to all reasons other than starting a new migraine prophylaxis treatment will have their data collected after discontinuation of study treatment, and those off-treatment data will be included in the analysis.

Detailed methods and procedures will be documented in the statistical analysis plan prior to study completion.

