10.5.5 Population-level Summary

The population-level summary for the primary endpoint is the difference in primary variable means between each atogepant group and placebo.

Participants are always analyzed based on their treatment assignment by randomization. To obtain the estimate of treatment effect defined in the off-treatment hypothetical estimand, an MMRM similar to the primary analysis specified in Section 10.2.1 will be performed on observed data collected from both double-blind treatment period and follow-up period. The model terms include treatment group, visit (derived as month), prior exposure (yes/no) to a migraine prevention medication with proven efficacy, treatment- by-visit interaction, the baseline score and baseline-by-visit interaction.

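### Minor, on the readable text: the off-treatment hypothetical estimand excludes only follow-up data after a new preventive starts, so double-blind diary days on that drug stay in.

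*SAP*

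**What the plan says.** Protocol 7.4.4 and SAP 10.5.4 give the same rule. The event is a new prophylactic started in the double-blind or the safety follow-up period. In the protocol such participants "will have their data during the safety follow-up period after starting the new migraine prophylaxis treatment excluded from the analysis"; the SAP says they "will have their data during the follow-up period after starting the new migraine prophylaxis treatment excluded from the analysis". SAP 17.11 also identifies takers in both periods.

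The treatment condition is wider than the exclusion. Protocol 7.4.1 states: "The protocol prohibits patients from starting any new migraine preventive treatments". SAP 10.5.1 gives the scope as "during the study (including the double-blind treatment period and the follow-up period)".

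The MMRM for this estimand "will be performed on observed data collected from both double-blind treatment period and follow-up period" (SAP 10.5.5). For 50% responders, SAP 10.5.6 also uses both periods and adds: "Data after participants started a new prophylaxis treatment during the follow-up period will be excluded". Protocol 7.4.6 says that the responder endpoint "will be derived using both on-treatment and off-treatment observed data as defined in the primary endpoint above".

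On the role of this analysis, Protocol 7.3.1.1 lists the MMRM on both periods among the sensitivity analyses for missing data ("The details for this analysis are provided in Section 7.4"), and SAP 10.2.3 does the same. SAP 10.5.6 also runs the graphical multiplicity procedure on it. Protocol 7.1 attaches the word primary to the matching population, but part of that sentence is redacted.

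**The concern.** The event window covers two periods and the exclusion covers one. A participant who starts a preventive in Week 5 and stays in the double-blind period contributes diary days on that drug. Days on the same drug are dropped once follow-up begins. No readable passage gives a reason for the difference.

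The estimand describes the effect with no new preventive in either period. For the affected participants, the data analysed do not meet that condition. If starters are commoner on placebo, the estimated difference shrinks. If they are commoner on atogepant, it grows. If they are balanced, nothing moves.

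**Working it through.** **Reading the rule.** I looked for readable text that removes double-blind days after the start and found none. In SAP 10.5.6 the phrase about the follow-up period can attach to the start or to the data. If it attaches to the start, even follow-up data after a double-blind start would stay in. Protocol 7.4.6 only refers back to the primary rule.

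**When follow-up begins.** The second rule in SAP 10.5.4 treats starting a preventive as one possible reason for stopping study treatment. Protocol 8.8 and 8.9 allow discontinuation for a protocol deviation and withdrawal where results may be confounded. No readable passage makes the move immediate. New medication is asked about at visits (Protocol 8.7), which fall at Weeks 2, 4, 6, 8 and 12 (Protocol 3).

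**Planning figure.** Inputs from SAP 15: 218 per arm, difference 1.5 days, SD 3.5, two-sided alpha 0.0167. SE = 3.5 × √(2/218) = 0.335 day. The two-sample t power is 98.1%, against the plan's 98%.

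**Share of data affected.** Assumptions: start day uniform over Days 1-84 and complete diaries.

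*Starter moves to follow-up at the next visit.* Later data are then excluded. A month needs 14 retained days and is prorated. The mean number of post-start days is 7.5 in a 14-day visit interval and 14.5 in a 28-day one.

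| Start days | Affected part of that month | Divided by 3 months | Divided by own evaluable months |
|---|---|---|---|
| 1-14 | 7.5/14 = 0.536 | 0.179 | 0.536 (1 month) |
| 15-28 | 7.5/28 = 0.268 | 0.089 | 0.268 (1 month) |
| 29-42 | 7.5/14 = 0.536 | 0.179 | 0.268 (2 months) |
| 43-56 | 7.5/28 = 0.268 | 0.089 | 0.134 (2 months) |
| 57-84 | 14.5/28 = 0.518 | 0.173 | 0.173 (3 months) |

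With weights 1/6 for each of the first four rows and 1/3 for the last, the shares are 0.15 (three months) and 0.26 (own evaluable months). The MMRM's weighting need not equal either, so I use both as a rough range.

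*Starter stays to Week 12.* Mean share = 42.5/84, about 0.5.

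**Bias** = net excess of starters in one arm × preventive effect × share. Assumed, not in the documents: excess 1-3% (about 2-7 of 218) and effect 1.5-3 days per month.
- Next visit, low end: 0.01 × 1.5 × 0.15 = 0.002 day.
- Next visit, high end: 0.03 × 3 × 0.26 = 0.023 day.
- Stay to Week 12, low end: 0.01 × 1.5 × 0.5 = 0.008 day.
- Stay to Week 12, high end: 0.03 × 3 × 0.5 = 0.045 day.

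The largest of these is 0.045/1.5 = 3% of the planned difference and 0.045/0.335 = 0.13 SE. If it all runs toward the null, the detectable difference is 1.455 days and power is 97.3%.

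**Responders.** The planned odds ratio is (0.50/0.50)/(0.33/0.67) = 2.03. Suppose 1-3% excess placebo starters have a response rate of 50% instead of 33%. The placebo rate becomes 0.33 + 0.01 × 0.17 = 0.3317 or 0.33 + 0.03 × 0.17 = 0.3351, and the odds ratio becomes 2.01 or 1.98.

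**The case against.** The strongest reply is that the rule is deliberate. Protocol and SAP agree on it. The primary MMRM (SAP 10.2.1) uses double-blind data, and its readable text has no exclusion for a new preventive. Screening only the added follow-up data keeps the double-blind data identical in the two analyses, so any difference between them comes from off-treatment data alone. That is a sensible aim, but no readable passage states it, and it leaves the rule at odds with the estimand's own treatment condition.

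The second reply is redaction, and it stands as a limit. The sentence that introduces the estimand is cut in both documents. Text in SAP 10.5.2, the visit-window tables in SAP 17.1, the eDiary derivation in SAP 17.2.1 and most of Protocol 4.4.2 are also unreadable. A prompt stop of study treatment, or a further exclusion, could be there.

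Third, SAP 10.5.4 expects only a few such participants, as protocol deviators. That also stands, and it is why the point is minor.

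A reader might infer that the primary result is affected, or that the rule favours atogepant. The documents support neither. The point concerns this estimand only, and nothing shows which arm would have more starters.

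**Conclusion.** The point holds as a minor one, on the readable text and with medium confidence. The exclusion is narrower than both the event definition and the treatment condition.

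The direction of any bias is unknown. Its size is about 0.002-0.023 day if starters move to follow-up at the next visit and 0.008-0.045 day if they stay to Week 12. These ranges rest on the assumed excess, preventive effect and uniform start times. The trial's conclusion is unlikely to change.

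Two stronger readings fail. The protocol and SAP do not contradict each other on the exclusion: they share the same gap. Nor can it be said that double-blind days certainly remain, given the redactions. Whether this analysis is purely a sensitivity analysis is also not settled by the readable text.

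**What to change.** **Change.** In SAP 10.5.4 and Protocol 7.4.4, exclude all eDiary data recorded on or after the start date of the new preventive, in either period. Apply the existing 14-day and proration rules to the affected month. Use the same wording in SAP 10.5.6. If the protocol is not amended, record the change in SAP Section 19, which now lists none. Keep the observed-data MMRM as specified.

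For this filter, query partial start dates instead of defaulting to SAP 17.8. When month and day are both missing in the year of first dose, SAP 17.8.2 assigns the first-dose date, which would remove all three months.

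**Alternative.** If the double-blind days are kept on purpose, say so and reconcile Protocol 7.4.1 and SAP 10.5.1 with Protocol 7.4.4 and SAP 10.5.4 and 10.5.6.

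**Cost.** Wording, one date filter and a few queries; no new data collection. With uniform start days, starts on Days 1-14, 15-42, 43-70 and 71-84 lose 3, 2, 1 and 0 months, a mean of (14 × 3 + 28 × 2 + 28 × 1)/84 = 1.5. Assuming 1-3% starters within an arm (a different quantity from the net excess above), 218 × 0.01 × 1.5 = 3.3 to 218 × 0.03 × 1.5 = 9.8 of 654 participant-months per arm become missing, or 0.5-1.5%. The MMRM treats them as missing at random. The double-blind data of these few participants would also differ from those in the primary MMRM.
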